4.3 Definitions

Study Eye 1 (SE1) is defined as the first treated eye (within GEMINI or in an antecedent clinical trial). **Study Eye 2 (SE2)** is defined as the second treated eye (irrespective of whether the first eye was treated in GEMINI or in an antecedent clinical trial). Subjects whose first eye is treated in an antecedent study will contribute to Period 2 only (except for the immunogenicity analyses), where Study Eye 1 is the eye treated in the antecedent study and Study Eye 2 is the eye treated in GEMINI.

Period 1 starts on the day of the surgery of the first treated eye and ends on the day prior to the day of the surgery of the second treated eye. **Period 2** starts on the day of the surgery of the second treated eye.

Baseline Value of Period 1/2 is defined as the last non-missing value prior to treatment of the respective period. Baseline of each period for each eye will be used to calculate the change from baseline for the data in the same period and same eye. For example, period 1 SE1 baseline will be used to calculate the change from baseline for all the data of SE1 in period 1, whereas period 2 SE1 baseline will be used to calculate the change from baseline for all the data of SE1 in period 2.

For immunogenicity, baseline will be defined separately in [Section 4.17.11](#).

Analysis day for all the post-baseline visits will be calculated as the date of the post-baseline visits minus the corresponding injection date, depending on which baseline that was used.

For the 6 subjects whose first eye was treated in the antecedent study (Subjects [REDACTED], [REDACTED], [REDACTED]), only period 2 data are collected in GEMINI. Therefore, only period 2 data will be presented for these 6 patients.

Change from Baseline is defined as the difference of the value of an assessment at the considered visit from the baseline value of the corresponding period.

Duration is measured in days and is calculated as end date – onset date + 1.

Injection dates of SE1 and SE2 will be coded **Day 0** for the Period 1 and Period 2 respectively.

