8.1 Inclusion Criteria

During the Screening Period, subjects will be found eligible for study participation if they meet all of the following inclusion criteria.

1. Are willing and able to give informed consent for participation in the study to have both eyes treated
2. Are male and ≥ 18 years of age
3. Have documentation of a genetically-confirmed diagnosis of CHM
4. Have active disease clinically visible within the macular region of both eyes
5. Have a BCVA of ≥ 34 ETDRS letters (20/200 or better Snellen acuity) in both eyes, or in the untreated eye, if the other eye was previously treated with AAV2-REP1*

*If previously treated with AAV2-REP1 in an antecedent study, subjects may be eligible for participation following Sponsor approval.

6. For subjects who received treatment with AAV2-REP1 in an antecedent study, have biological samples available to complete an adequate immunology profile

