4.4 Data of Subjects with First Eye Treated in an Antecedent Study

For the 6 subjects who received timrepigene emparvovec treatment in their first eye in an antecedent study, the data from the antecedent study will not be included in the analyses presented in the Clinical Study Report (CSR).

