4.17.11.1 Baseline Definition

As the second eye treatment in Period 2 in GEMINI may potentially increase the risk of a subject developing an immune response against the therapeutic product, BIIB111, we define two different types of baselines to evaluate the treatment emergent immune response, anchored to the time when the first eye was treated, and when the second eye was treated, respectively. The definition is as below.

Period 1 baseline is defined as the last available value prior to surgery of the first eye. For subjects without any assessments prior to surgery of the first eye, Day 1 sample will be used as baseline. If neither assessment prior to surgery of the first eye nor Day 1 sample are available, the period 1 baseline is set missing.

Period 2 baseline is defined as the last available value within 10 weeks prior to the surgery of the second eye. For subjects without any assessments within 10 weeks prior to surgery of the second eye, Day 1 sample post-second eye surgery will be used as baseline for period 2. If neither assessment prior to surgery of the second eye nor Day 1 sample are available, the period 2 baseline is set missing.

Note that the immunogenicity data is collected as one record per subject per visit.

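### The SAP both keeps and excludes the antecedent-study immunogenicity data of six subjects; if exclusion governs, they lose the Period 1 immune baseline and could be misplaced in the immunogenicity–safety comparison

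*SAP*

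**What the plan says.** Three statements in the SAP govern the same six subjects.

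- SAP 4.3, first paragraph: they "will contribute to Period 2 only (except for the immunogenicity analyses".
- SAP 4.3, later paragraph: GEMINI collects only Period 2 data on them, so "only period 2 data will be presented for these 6 patients". No exception is made for immunogenicity.
- SAP 4.4 says of the same six that "the data from the antecedent study will not be included in the analyses presented in the Clinical Study Report". Again there is no exception.

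For immunogenicity, SAP 4.17.11.1 sets the baseline by period. "Period 1 baseline is defined as the last available value prior to surgery of the first eye". The Day 1 sample is the fallback, and if neither exists, "the period 1 baseline is set missing". The Period 2 baseline is separate: the last value in the 10 weeks before second-eye surgery, again with Day 1 as fallback.

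SAP 4.17.11.4 relates assay status to ocular inflammation, reduced visual acuity and hypersensitivity events, and to a loss of 15 or more letters at Month 12. It uses four strata: (1) negative and (2) positive at the Period 1 baseline; (3) some and (4) no treatment-emergent positive result during the study.

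Protocol 8.1, criterion 6, admits these subjects only if they "have biological samples available to complete an adequate immunology profile". Protocol 7.1 ties that profile to treatment of the first eye in the previous study.

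**The concern.** The exception in SAP 4.3 has content only if first-eye immunogenicity data from the antecedent study are used. The other two statements forbid that. A programmer cannot follow all three, and the choice decides how six subjects appear in the immunogenicity tables.

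This is not a side analysis. Protocol 13.1 and SAP 3.6 justify the sample size by the immunological profile of bilateral administration and call it the main concern in re-administration. What the first exposure did to a subject's immune status is central to that question. These six were admitted on condition that samples bearing on it existed.

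**Working it through.** **The plan's own figure.** 60 subjects × 2 eyes = 120 treated eyes, as stated in Protocol 13.1 and SAP 3.6. There is no power calculation to reproduce. If the six are among the 60, the eyes treated within GEMINI number 54 × 2 + 6 = 114.

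**What follows if SAP 4.4 governs.**

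1. Period 1 baseline. Both permitted samples (before first-eye surgery, or Day 1 after it) date from the antecedent study. Excluding that study's data makes the baseline missing.
2. Period 1 results. SAP 4.17.11.3 derives them from Period 1 visits against the Period 1 baseline. The six have neither.
3. Strata (1) and (2). Both are defined by Period 1 baseline status, so the six fit neither, and their Period 2 events leave that comparison.
4. Strata (3) and (4). SAP 4.17.11.3 sets treatment-emergent status to missing visit by visit when samples are lacking. SAP 4.17.11.4 does not say what that does to a subject's stratum, so the six can be classified on Period 2 data alone.
5. Misclassification in step 4. Take two subjects who both became positive after the first eye, stayed positive and showed no further rise after the second.

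| | First eye treated in GEMINI | First eye treated in an antecedent study, data excluded |
|---|---|---|
| Period 1 conversion | seen, treatment-emergent | not seen |
| Status at Period 2 baseline | positive | positive |
| Needed in Period 2 for treatment-emergent status, ADA or Nabs | titre at least 4 times baseline | titre at least 4 times baseline |
| Needed in Period 2, ELISpot | not possible for an analyte already positive | not possible for an analyte already positive |
| Stratum | (3) | (4) |

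The same immune history gives opposite strata.

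**Size.** Inputs: 6 antecedent subjects (SAP 4.3, 4.4), about 60 planned subjects (SAP 3.6), about 20 per surgery window (SAP 3.1). The precision measure is the Clopper-Pearson 95% upper limit for zero events, 1 − 0.025^(1/n); SAP 4.2 specifies Clopper-Pearson for percentages.

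- Overall: 6/60 = 10%, leaving 60 − 6 = 54. The upper limit moves from 6.0% (n = 60) to 6.6% (n = 54).
- Within one window: the documents do not say which window any of the six belongs to. If k of them fall in a 20-subject window, the share affected is k/20.

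| k | Share affected | With a Period 1 baseline | Zero-event upper limit |
|---|---|---|---|
| 0 | 0% | 20 | 16.8% |
| 3 | 15% | 17 | 19.5% |
| 6 | 30% | 14 | 23.2% |

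**Does another passage settle it?** SAP 4.20 lists changes from the protocol and does not mention these data. SAP 4.1 requires a baseline sample for the Immunogenicity set but does not say for which period.

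**The case against.** The strongest reply is that two explicit statements point to exclusion against one parenthesis, which may be a leftover. On that view the repair is to delete the parenthesis. This is a legitimate way to resolve the text, but it leaves the stratum problem unless SAP 4.17.11.4 is also changed.

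Four stronger readings are tempting, and the documents do not support them.

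- *The six drop out of the immunogenicity analyses.* They do not. Immunogenicity sampling is part of GEMINI screening (Protocol 10.1), so they can have a Period 2 baseline. They can enter the Immunogenicity set through it and contribute Period 2 treatment-emergent results by window. That baseline also records their immune status going into the second surgery.
- *The protocol required a first-eye immune baseline.* It requires that samples be available for an adequate profile related to first-eye treatment. It does not use the word baseline or promise analysis in this report, and Protocol 11.4.2 says that selected samples will be analysed.
- *The six are all in the long window, so 30% of it is lost.* No interval is given for any of them; 30% is the maximum of a range that starts at 0%.
- *SAP 4.3 expressly keeps them in Period 1 immunogenicity analyses.* It does not name Period 1. That is the only workable reading of the exception, but it is a reading.

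It is also fair that samples are not assay results. Whether the antecedent samples were tested, and by comparable assays, cannot be learned from these documents.

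**Conclusion.** The contradiction is real, sits in the current SAP text and is not resolved elsewhere. If exclusion governs, the loss is confined to the Period 1 baseline, Period 1 immunogenicity results and strata (1) and (2). In addition, first-eye responders among the six may be misplaced in stratum (4).

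The effect is modest overall: 10% of planned subjects, and a zero-event upper limit of 6.6% instead of 6.0%. It could be concentrated in one window, anywhere from 0% to 30%. These figures assume that the six are among the planned 60 and that windows fill at 20 each; actual enrolment is not given. All analyses are descriptive, so no test is invalidated. The matter should still be settled before the tables are produced, because a misplaced responder blurs the contrast between strata (3) and (4).

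**What to change.** Preferred:

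- Amend both SAP 4.4 and the later sentence of 4.3 to except immunogenicity. Amending 4.4 alone would leave 4.3 contradicting itself.
- Use existing antecedent-study immunogenicity results, from the samples required by Protocol 7.1 and criterion 6, for the Period 1 baseline and Period 1 visits. Do so only where the results are evaluable and the assays comparable.
- Flag the six subjects in the tables.
- State in SAP 4.1 which period's baseline admits a subject to the Immunogenicity set.

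If those results are not usable:

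- Delete the exception in SAP 4.3 and record the exclusion in SAP 4.20.
- Report the six separately in SAP 4.17.11.4, and do not place them in stratum (4) on Period 2 data alone. The SAP 4.1 clarification is still needed.

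The preferred route costs a few sentences, a data transfer and an assay-comparability check for six subjects, and possibly testing of stored samples not yet assayed. The alternative costs text and a separate row or listing.

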4.16.1 Visual Acuity

Best-corrected visual acuity (BCVA) and change from baseline will be summarised by visit, by eye, by period as well as overall. The corresponding 95% CIs will be calculated (See [Section 4.2](#)).

Furthermore, the proportion of eyes with a ≥ 10 letters increase, a ≥ 15 letters increase, and an increase or a loss < 5 letters (i.e. change from baseline > -5 letters) will be summarised by visit, by eye, by period as well as overall. The corresponding 95% CI will be presented (See [Section 4.2](#)).

The above main analyses will use the observed case method only. Imputation using LOCF method regardless of the reasons of missing data will be performed for supportive analyses (See [Section 4.8](#)).

In addition to the by-period, by-eye presentation mentioned above, as supportive analyses, for both continuous and categorical endpoints, the period 2 Study Eye 1 data will be presented by

remapping them to visits after their last visit in period 1 and calculating change from baseline using baseline at period 1 for the same eye (Study Eye 1). This way a full picture of Study Eye 1 treatment journey during the entire study will be presented.

For all assessments of periods 1 and 2 of Study Eye 1, the data records will be assigned to calculated visit window (using study day) as described in [Table 2](#) below. The window of the visits following baseline (including unscheduled visits) will be constructed in such a way that the upper limit of the interval falls half way between the two visits.

If a patient has more than one assessment included within a window, the assessment closest to the target day will be used. In case of ties between observations located on different sides of the target date, the value with the later date will be used.

Table 2 **Visit Assignment Windows**

Day / Month	Target Day	Day Range included in the visit
Baseline	0	The last assessment on or before day 0
Day 1	1	Day 1
Day 3	3	Day 2 to 5
Day 7	7	Day 6 to 10
Day 14	14	Day 11 to 22
Month 1	30	Day 23 to 61
Month 3	91	Day 62 to 136
Month 6	182	Day 137 to 272
Month 9	273	Day 228 to 318
Month 12	365	Day 319 to 410
Month 15	456	Day 411 to 501
Month 18	548	Day 502 to 593
Month 21	639	Day 594 to 684
Month 24	731	Day 685 onwards

Both continuous and categorical endpoints for BCVA will be summarised by subgroups mentioned in [Section 4.7](#).

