4.17.8 Fundus Photography

Presence and severity of Retinal Pigment Epithelium (RPE) Hyperplasia, Retinal Arteriolar Narrowing, Retinal Vessel Sheathing, Optic Atrophy/Pallor and Optic Disc Swelling will be summarised by visit, by eye, and by period. Shift from baseline will also be evaluated.

The categories for the shift from baseline are defined as follows:

- Absent at Baseline to absent
- Absent at Baseline to present
- Present at Baseline to absent
- Present at Baseline to present

where Absent corresponds to None and Present to Mild, Moderate or Severe.

Image quality will be listed only. This includes image completeness, focus/clarity, field definition, stereopsis, exposure and contrast.

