4.17.11.4 Relationship Between Immunogenicity Assay and Safety

The relationship between the immunogenicity assays (ADA, Nab and ELISpot) and selected adverse events will be assessed. These adverse events include ocular inflammation-related adverse events, visual acuity reduced-related adverse events and hypersensitivity-related adverse events. The number and percentage of post-treatment (treatment-emergent) ocular inflammation-related adverse events, visual acuity reduced-related adverse events and hypersensitivity-related adverse events (based on the adverse event data), as well as the number and percentage of eyes with a decrease from baseline of ≥ 15 letters in BCVA at Month 12 (based on the visual acuity assessment data) will be summarized by (1) subjects with negative assay at period 1 baseline; and (2) subjects with positive assay at period 1 baseline; and (3) subjects with at least one treatment-emergent positive assay at any visit during the study; and (4) subjects with no treatment-emergent positive assay during the study. In (3) and (4), to determine the treatment-emergent positivity, the period 1 baseline will be used to calculate the change from baseline for data in period 1 and period 2 baseline will be used to calculate the change from baseline for data in period 2.

The analyses will be conducted by eye, by period and surgery window. It will be repeated by AE severity (mild, moderate and severe) and by AE time to onset (≤ 30 days and > 30 days post-surgery). If an AE has more than one occurrence with an onset ≤ 30 days and another > 30 days, the AE will be reported in both ≤ 30 days and > 30 days' time to onset categories.

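### The supportive return of SE1 to its own pre-treatment baseline covers BCVA only; other ocular endpoints and the assay-by-vision-loss count lack it, and Table 2 overlaps

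*SAP*

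**What the plan says.** - **Periods and baselines (SAP 4.3).** The first of the two periods is bounded by the two operations: it "starts on the day of the surgery of the first treated eye and ends on the day prior to the day of the surgery", meaning here the SE2 operation, and Period 2 begins with that operation. Baseline is the last non-missing value before treatment in the period concerned. For SE1 the consequence is spelt out: "whereas period 2 SE1 baseline will be used to calculate the change from baseline for all the data of SE1 in period 2". Change from baseline is defined generally against the baseline of the same period. Protocol 13.4 likewise defines baseline by eye and by period.
- **The exception for BCVA (SAP 4.16.1).** As a supportive analysis, Period 2 SE1 records are moved onto the SE1 timeline, "calculating change from baseline using baseline at period 1 for the same eye". SAP 4.17.1 puts the losses of 5, 10 and 15 or more letters in the same tables, so the remap reaches them.
- **Other ocular endpoints (SAP 4.16.2 to 4.16.4, 4.17.2 to 4.17.5, 4.17.8).** AF, SD-OCT, microperimetry, IOP, slit lamp, lens grade, ophthalmoscopy and fundus photography are presented by visit, eye and period, some also overall, with no remap. The fundus photography list, for example, ends: "Optic Disc Swelling will be summarised by visit, by eye, and by period. Shift from baseline will also be evaluated".
- **Vision loss and immunogenicity (SAP 4.17.11.4).** Eyes down 15 or more letters at Month 12 are counted by assay status. "The analyses will be conducted by eye, by period and surgery window". A baseline is named for the assays but not for BCVA.
- **Visit windows (SAP 4.16.1, Table 2).** The stated rule is that "the upper limit of the interval falls half way between the two visits". Month 6 is given as Day 137 to 272 and Month 9 as Day 228 to 318.
- **Six antecedent subjects.** SAP 4.4 says "the data from the antecedent study will not be included in the analyses presented in the Clinical Study Report". SAP 4.3 restricts these subjects to Period 2 but exempts the immunogenicity analyses.

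**The concern.** The study asks whether treating both eyes in sequence is safe, with at least 12 months of follow-up per eye. Once SE2 is operated on, the SE1 reference value is reset to one taken after SE1's own surgery. Any SE1 change that arose before that point drops out of the Period 2 change and shift tables. The SAP recognises this for BCVA by adding the remap, but gives no counterpart for the other ocular safety measures, and SAP 4.20 does not discuss the difference.

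The Period 1 Month 12 row for SE1 does not fill the gap. It holds long-window subjects plus any whose SE2 surgery was postponed or withheld. Protocol 7.1 and 8.3 let the SE1 outcome influence both, so the row can be selected on the outcome it reports.

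In 4.17.11.4, SE1 loss before SE2 surgery goes uncounted mainly in the short and medium windows, and surgery window is one of the strata of that analysis.

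**Working it through.** **1. The plan's own figures.** SAP 3.1 plans about 20 subjects in each of three windows: 3 × 20 = 60 subjects, 60 × 2 = 120 eyes. Both match SAP 3.6.

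**2. Subjects whose SE1 Month 12 follows SE2 surgery.**
- Short plus medium: 20 + 20 = 40; 40/60 = 67%.
- Visit 9 opens at Day 365 − 14 = 351, so medium-window surgery on Days 352 to 365 could follow it. If medium gaps are spread evenly over Days 182 to 365, that is 14/184 = 7.6%, or 1.5 of 20 subjects.
- Protocol 10.1 asks sites to align SE2 surgery with a planned Period 1 visit. If every medium-window surgery followed the Month 12 visit, the figure would be 20/60 = 33%.
- The range is therefore 20 to 40. It concerns SE1 Month 12 only. At later Period 2 visits the 4.3 rule affects SE1 in everyone treated in both eyes, of whom up to 60 − 6 = 54 have a Period 1 baseline in this study.

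**3. How many a remap can serve.** The six antecedent SE1 eyes have no pre-treatment value in the analyses under 4.4. If all six are long-window, 40 remain repairable; if all are short or medium, 40 − 6 = 34. In the lower case of 20 affected, 20 − 6 = 14 to 20 remain. Overall: 14 to 40.

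**4. Effect on the 15-letter count (illustration).** Take SE1 at 70 letters before treatment, 60 before SE2 surgery and 54 at Period 2 Month 12.
- Own baseline: 54 − 70 = −16, counted.
- SAP 4.3: 54 − 60 = −6, not counted.
- In general, a loss of L letters before SE2 surgery raises the own-baseline loss needed to be counted from 15 to 15 + L.

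**5. Whether a remapped Month 12 value exists.** SE1 day = gap + Period 2 visit day, with nominal days 1, 3, 7, 14, 30, 91, 182 and 365. The Month 12 window is Day 319 to 410.
- Visit 9 falls inside if gap + 365 ≤ 410, so gap ≤ 45. Visit 8 falls at Day 319 or later if gap + 182 ≥ 319, so gap ≥ 137.
- Gaps of 46 to 136 days therefore miss the window: 91 of the 168 days from 14 to 181, or 54%. That is about 11 of 20 short-window eyes if gaps are evenly spread. Medium gaps do not miss it.
- With visit tolerances, no scheduled visit can fall in the window for gaps of 60 to 122 days.
- Defaulting to the next later visit is not a safe repair. At a gap of 130 days it takes Day 130 + 365 = 495, although Day 130 + 182 = 312 is nearer to Day 365. Later is further for all gaps of 92 to 136 days.

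**6. Fundus photography.** Photographs are scheduled at Screening, Period 2 Baseline, Visit 9 and early termination. The SE1 shift at Period 2 Visit 9 is taken from the Period 2 Baseline photograph, after SE1 surgery, unless the gap is short enough for Screening itself to serve. For gaps of 14 to 365 days, that Visit 9 falls at about SE1 Day 14 + 365 = 379 to 365 + 365 = 730.

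**7. Table 2.** The midpoint of Months 6 and 9 is (182 + 273)/2 = 227.5, so Month 6 should end at Day 227. The overlap is 272 − 228 + 1 = 45 days. On nominal days a Period 2 visit falls in it for gaps of 46 to 90, 137 to 181 and 198 to 271 days: 90/168 = 54% of short gaps and 74/184 = 40% of medium gaps, if evenly spread.

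**The case against.** The period baselines are deliberate. They follow Protocol 13.4 and isolate what happens to the first eye after the second is dosed, which matters because SAP 3.6 names re-administration as the key concern. SAP 4.17.11.1 pairs each period with its own assay baseline, so a Period 2 BCVA baseline in 4.17.11.4 is coherent. SAP 4.20 says the main purpose is to evaluate BCVA from a safety perspective, a plausible reason for remapping only BCVA. The study is descriptive, and other outputs carry information: raw values by visit, listings, Period 1 tables up to SE2 surgery, and per-eye AE summaries by period and window that depend on no analysis baseline.

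Most of this stands. It argues for keeping the by-period tables and the by-period count, and it limits the gap. It does not close it. Raw values and AEs do not give change or shift from the pre-treatment state, and Protocol 11.1.1.1 excludes worsening consistent with choroideremia progression from AEs. The overall columns do not help, because change is still defined within period. The wording in 4.16.1 about all SE1 assessments could be read more widely, but it assigns visit windows, sits under Visual Acuity, and no other section refers to it.

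A reader might infer that SE1 loss of 15 or more letters from its own baseline is never reported. That is not so: 4.17.1 places it in the 4.16.1 tables, and BCVA is also summarised by surgery window. Only the cross-tabulation with assay status lacks it.

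**Conclusion.** The gap is real, limited and worth fixing. For the non-BCVA ocular endpoints, no planned change or shift table shows SE1 at 12 months after its own surgery against its pre-treatment state in about 40 of 60 planned subjects (20 to 40; 14 to 40 repairable). The 4.17.11.4 count misses SE1 loss that preceded SE2 surgery. Table 2 is wrong by its own rule.

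The figures rest on the planned 20/20/20 split, on month boundaries taken as Days 182 and 365, and, where stated, on evenly spread gaps, nominal visit days and no dropout. The SAP gives no actual counts by window.

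Two stronger readings are not supported. The by-period baseline is not itself an error, since it follows the protocol and answers a relevant question. Nor is SE1 harm invisible, given the raw values, listings, Period 1 tables, AE summaries and remapped BCVA tables.

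**What to change.** 1. Extend the 4.16.1 SE1 own-baseline remap to the other ocular endpoints as supportive tables beside the by-period tables, which stay. Tabulate the SE1 Period 2 Baseline and Period 2 Visit 9 photographs against Screening, with the actual SE1 day. List the addition in 4.20.
2. In 4.17.11.4, keep the count by period baseline and state that baseline. Add a second count of loss of 15 or more letters from SE1's own pre-treatment baseline, using the Day 319 to 410 window. Report SE1 eyes with no visit in that window as not evaluable at Month 12, by surgery window. Any count using an out-of-window visit should be a separate sensitivity count showing the actual day. Reconcile the immunogenicity exemption in 4.3 with 4.4 for the six antecedent subjects; under 4.4 their SE1 eyes have no pre-treatment BCVA for the added count.
3. Correct Table 2 so that Month 6 is Day 137 to 227.

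The cost is SAP wording and more tables, using a method already planned for BCVA. No new data or visits are needed. The drawback is that SE1 visit days after SE2 surgery are irregular, and a sizeable share of short-window eyes may have no Month 12 value.
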